### **Interaction with Dabigatran**

To assess the effect of dabigatran on LT3001, a linear mixed-effects model with Day (Day 1 and Day 5) as a fixed effect, and subject as a random effect on log PK-parameters will be used to calculate 90% confidence intervals (CIs) for the geometric mean ratios (GMRs) of  $AUC_{0-t}$ ,  $AUC_{0-\infty}$ ,  $C_{max}$ , and  $C_{trough}$  by exponentiating the Least Square Mean Differences. The criteria of 90% CI within 50-200% of weak-effect boundaries will be used first for assessment. Only when the first criteria are satisfied, the second criteria of 90% CI within 80%-125% of no-effect boundaries will be used for further assessment.

The effect of LT3001 on the PK of dabigatran will be assessed by comparing PK parameters of dabigatran with and without LT3001 using a linear model similar to above with Day (Day 4 and Day 7) as fixed effect. PK parameters for comparison include  $AUC_{(0-t)}$  and  $C_{max}$ .

## **8.4. Urine PK: Part A only**

### **Urine PK Concentration**

Urine concentrations of LT3001 and concomitant medications will be summarized with descriptive statistics (n, arithmetic mean, SD, CV%, minimum, median, and maximum) by treatment in Part and cohort and listed by subject.

### **Urine PK Parameters**

The following urine PK parameters will be calculated for Part A:

- $A_{ex-y}$ : Amount of drug excreted in urine within a collection interval (x to y hours), where the values of x to y are 0 to 12 and 12 to 24
- $Ae_{0-24}$ : Total amount of drug excreted in urine over the entire collection period (0 to 24 hours)
- $Fe_{0-24}$ : Fraction excreted in urine from 0 to 24 hours after dosing, calculated as  $Ae_{0-24} / Dose \times 100$
- $CLR$ : Renal clearance, calculated as  $Ae_{0-24} / AUC_{0-\infty}$

---

Urine PK parameters of LT3001 will be summarized with descriptive statistics (n, arithmetic mean, SD, CV%, minimum, median, and maximum) by treatment and listed by subject.

## 9. SAFETY ANALYSIS

Safety analyses will be performed on the SAS. Part A and Part B safety results will be presented separately. Part A data will be summarized by treatment and Part B data will be summarized by cohort.

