#### 10.3.1. Safety Analyses

All safety analyses will be performed on the Safety Analysis Set. Adverse events will be coded by System Organ Class and Preferred Term using the latest version of MedDRA. Incidences of TEAEs (ie, events that started after exposure to study drug or worsened in severity after dosing) will be presented by dose group, maximum severity, and relationship to study medication.

Safety data will be summarized through appropriate data tabulations and standard descriptive statistics by treatment. For each continuous laboratory parameter, results will be categorized as low, normal, or high based on the laboratory normal ranges. Shift tables capturing the number and percentage of subjects shifting from these baseline to post-baseline categories will be presented.

The association of AEs, laboratory results, coagulation parameters, platelet function test, vital sign measurements, oximetry, and ECG results with the treatment of study drug or PK parameters may also be explored. If appropriate, statistical modeling will be performed to further characterize the associations mentioned above. All out-of-range and clinically significant laboratory results will be identified in subject data listings. The number and percentage of subjects in each dose group with normal and abnormal physical examination results will be presented for evaluations at baseline and final visit.

For each body system, changes in the subjects' findings from baseline to final visit (no change, normal to abnormal, or abnormal to normal) will be tabulated for each dose group.

To investigate whether platelet function test is prolonged when coadminstrated with LT3001 drug product, platelet function test observed under single treatment of aspirin, clopidogrel, apixaban or dabigatran will be compared with platelet function test observed under coadministration with LT3001 drug product. Platelet function test will be summarized with standard descriptive statistics by treatment. Shift tables capturing the number and percentage of subjects shifting from baseline to post-baseline categories will be presented.

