## **2. INTRODUCTION**

The purpose of this statistical analysis plan (SAP) is to prospectively outline in detail the data derivations, statistical methods, and presentations of data so that valid conclusions can be reached to address the study objectives outlined in the protocol LT3001-105, dated 17 November 2020.

This SAP is written with due consideration of the recommendations outlined in the most recent International Conference on Harmonization (ICH) E9 Guideline entitled Guidance for Industry: Statistical Principles for Clinical Trials and the most recent ICH E3 Guideline entitled Guidance for Industry: Structure and Content of Clinical Study Reports (CSR).

The planned analyses identified in this statistical analysis plan (SAP) may be included in regulatory submissions and/or future manuscripts. Exploratory analyses, not identified in this SAP, may be performed to support the clinical development program. The statistical analysis methods presented in this document will amend and/or supersede the statistical analysis methods described in the protocol. Any post-hoc or unplanned analyses that are performed but not identified in this SAP will be clearly identified in the CSR.

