### 6.4. Subgroup Analyses

Although no subgroup analyses are planned, Part A results will be presented by treatment (LT3001 and placebo) and population (Chinese and Non-Asian) and Part B results will be presented by cohort.

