### 9.1. Adverse Events

Adverse Events will be coded according to the latest version of the MedDRA dictionary. For this study, surveillance of adverse events (AE) will begin from Day 1 of the treatment period until the end of the follow-up or early termination.

Adverse events shall be recorded starting at signing of ICF. AEs will be defined as treatment-emergent adverse events (TEAE), if they occurred after administration of any study treatment or if they started prior to study drug administration but worsened after dosing, given that worsening started within the treatment period.

Only TEAEs shall be summarized in the clinical study report. An overall summary with number and percentage of subjects with all different TEAE categories, like treatment-related, serious, leading to withdrawal, and fatal will be provided. Incidence and severity of TEAEs will be summarized within System Organ Class (SOC), and within Preferred Term (PT).

TEAEs will be summarized by relationship per SOC and PT. Relationships will be categorized into related (includes “Related”, “Possibly Related” and “Probably Related”) and unrelated (includes “Not Related” and “Unlikely Related”).

TEAEs will also be summarized by maximal severity per SOC and PT. To count the number of subjects with any TEAEs, if a subject has multiple TEAEs coded to the same PT within the same SOC, the subject will be counted once under the maximal severity.

All AEs will be listed by subject. Serious AEs (SAEs), TEAEs, and AEs leading to withdrawal will be flagged accordingly.

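### Part B adverse event tables are specified by cohort only, so they do not separate events that began before and after LT3001 was added to the marketed drug

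*SAP*

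**What the plan says.** SAP 9 sets the grouping for safety data: "Part A data will be summarized by treatment and Part B data will be summarized by cohort". SAP 6.4 says the same of results in general: "Part B results will be presented by cohort".

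SAP 9.1 calls events treatment-emergent "if they occurred after administration of any study treatment or if they started prior to study drug administration but worsened after dosing". The window is a single one: "surveillance of adverse events (AE) will begin from Day 1 of the treatment period until the end of the follow-up or early termination". Treatment-emergent events are tabulated by SOC and PT, by relationship and by maximal severity. For repeated events with the same PT, "the subject will be counted once under the maximal severity".

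Protocol 10.3.1 words the grouping differently: "Safety data will be summarized through appropriate data tabulations and standard descriptive statistics by treatment". Its sentence on treatment-emergent events says that incidences "will be presented by dose group, maximum severity, and relationship to study medication". SAP 2 gives the SAP precedence: "The statistical analysis methods presented in this document will amend and/or supersede the statistical analysis methods described in the protocol".

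Elsewhere the SAP does contrast the marketed drug alone with the combination. SAP 8.3 does so for the marketed drugs' PK, and SAP 9.2 does so for platelet function.

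**The concern.** The Part B objective (SAP 3.1) is safety and PK when LT3001 is given with each of four marketed drugs. Adverse events are a named Part B endpoint (SAP 3.2). Part B has no placebo, so each subject's days on the marketed drug alone are the only reference within the study for what changes when LT3001 is added to that drug.

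A table with one column per cohort does not use that reference. A subject whose event began on the marketed drug alone and a subject whose event began on the combination add the same amount to the same cell. Laboratory, vital sign and ECG results are summarised by visit, so a reader can place them before or after coadministration. The adverse event tables, as the SAP text specifies them, give no such handle. A reader would have to go back to the listings, with no stated convention for transition days, partial dates or events in follow-up.

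**Working it through.** **1. Is there a rule for treatment at onset?**

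| Place | What it settles | Places an event in a phase? |
|---|---|---|
| SAP 5, Safety Analysis Set | Analysis by treatment actually received, per subject | No; it cannot split one subject's successive treatments |
| SAP 6.1 | Study day and baseline | No |
| SAP 6.5 | Whether an event with a missing or partial start date is treatment-emergent | No |
| SAP 9.1 | Treatment-emergent definition, window, tables, counting | No |
| SAP 10 | Display and calculation conventions | No |
| Protocol 10.3.1 | Grouping by treatment, or by dose group for treatment-emergent events | No |

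**2. Planned days that one cohort column pools.** The inputs are the dosing days in SAP 4 and Protocol 5.1 and the follow-up visit days in Protocol 5.1. Days are counted inclusively from Day 1 to the planned follow-up visit.

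| Cohort | LT3001 alone | Marketed drug alone | Combination dosing | Follow-up | Total |
|---|---|---|---|---|---|
| 1 (aspirin) | Day 1 = 1 | Days 2-5 = 4 | Days 6-8 = 3 | Days 9-15 = 7 | 15 |
| 2 (clopidogrel) | Day 1 = 1 | Days 2-6 = 5 | Days 7-9 = 3 | Days 10-16 = 7 | 16 |
| 3 (apixaban) | Day 1 = 1 | Days 2-4 = 3 | Days 5-7 = 3 | Days 8-14 = 7 | 14 |
| 4 (dabigatran) | Day 1 = 1 | Days 2-4 = 3 | Days 5-7 = 3 | Days 8-14 = 7 | 14 |

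**3. Share of the window on combination dosing** = combination days / total days.
- Cohort 1: 3/15 = 20.0%.
- Cohort 2: 3/16 = 18.8%. Protocol Table 3 allows one day either side of the Day 16 visit, which gives 3/17 = 17.6% to 3/15 = 20.0%.
- Cohorts 3 and 4: 3/14 = 21.4% each.

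**4. Planned subject-days in Part B** at 12 subjects per cohort, all completing.
- LT3001 alone: 4 x 12 = 48.
- Marketed drug alone: 12 x (4 + 5 + 3 + 3) = 180.
- Combination dosing: 4 x 3 x 12 = 144.
- Follow-up: 4 x 7 x 12 = 336.
- Total: 48 + 180 + 144 + 336 = 708, of which combination dosing is 144/708 = 20.3%.

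**5. Does follow-up need its own column?** Merged with combination dosing, it would make a phase of 3 + 7 = 10 days against 4, 5, 3 and 3 days on the marketed drug alone. The ratios are 2.5, 2.0, 3.3 and 3.3. At a constant event rate the merged column would look worse through length alone. Kept apart, the dosing comparison is 3 days against 4, 5, 3 and 3.

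Follow-up is not free of drug either. Five half-lives, from the ranges in Protocol 5.1, are 5 x 9 to 14 h = 45 to 70 h for apixaban and 5 x 12 to 17 h = 60 to 85 h for dabigatran. Early follow-up events can therefore still fall under exposure to these drugs.

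**The case against.** The strongest reply has four parts.

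- **By cohort may already mean by treatment.** A reader might infer that the SAP contradicts Protocol 10.3.1. The documents do not support that. The synopsis lists the four Part B cohorts under Treatment Groups and Duration, each as a marketed drug with and without LT3001. Protocol 7.4 assigns subjects to treatment cohorts. The protocol's sentence on treatment-emergent events groups by dose group, and the protocol has no onset rule of its own. For platelet function and PK it uses treatment in the narrower sense, so the term is ambiguous for Part B. Even if there were a conflict, SAP 2 would decide precedence. This part of the reply stands.

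- **The tables may already be split.** SAP 12 puts the layouts in a separate Data Displays Document, which was not available. Grouping by cohort does not forbid columns within cohort: SAP 9.2 falls under the same sentence and still separates platelet function. This stands as a limit on the claim, which is only that the SAP text does not require the split or define it.

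- **Nothing is lost, and the phases are known.** Adverse events are listed by subject, and SAP 10.2 puts study treatment in the listings in general. A reader might infer that phase boundaries would be chosen after seeing the data. But the dosing days are fixed in both documents. Only follow-up, transition days and partial dates are open.

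- **Relationship tables cover the question.** They do so only in part. They rest on investigator judgement in an open-label part, SAP 9.1 does not say which drug the relationship refers to in Part B, and they do not show when an event began.

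**Conclusion.** The point holds as a gap in the SAP text. Part B treatment-emergent events are specified by cohort, with no rule for treatment at onset. Each column mixes three treatment conditions and follow-up, and combination dosing makes up about a fifth of the window (18.8% to 21.4% at planned visit days). Tables built to that text cannot separate events that began before LT3001 was added from those that began after, which is what the Part B objective asks about.

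It is not a proven departure from the protocol, and no data are lost. The documents contain no adverse event counts, so they do not show that any conclusion would change. The day counts show only what is pooled. They assume 12 completers per cohort and planned visit days. Letting the Cohort 2 visit move by one day either way changes total subject-days from 708 to between 696 and 720. The point concerns the adverse event summary tables only.

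**What to change.** In SAP 9 and 9.1, keep the by-cohort totals and add descriptive Part B summaries of treatment-emergent events, at least overall and by SOC and PT, by cohort and treatment at onset:

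1. Use four columns: LT3001 alone; marketed drug alone; combination dosing days; follow-up after the last dosing day.
2. Define the phases by the planned dosing days already in SAP 4.
3. Assign each event by onset date, and by time where recorded. If only the date is known on a transition day, use the later phase and footnote the number of such events.
4. Count an event that cannot be placed in the cohort total only, with a footnote.
5. Use subjects entering the phase as the denominator, and show subject-days because phase lengths differ.

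Make the Data Displays Document match, and say in the SAP how treatment and dose group in Protocol 10.3.1 are to be read for Part B.

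The cost is SAP wording and extra columns in the Part B table shells, with no new assessments. The documents do not show that onset times are captured, so the date-only rule may be needed often. The downside is sparse columns (one subject in 12 is 8.3%), a fixed order of phases, unequal lengths and carry-over of the marketed drug. The display should be labelled descriptive, and it does not by itself attribute an event to LT3001.

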### 9.1. Adverse Events

Adverse Events will be coded according to the latest version of the MedDRA dictionary. For this study, surveillance of adverse events (AE) will begin from Day 1 of the treatment period until the end of the follow-up or early termination.

Adverse events shall be recorded starting at signing of ICF. AEs will be defined as treatment-emergent adverse events (TEAE), if they occurred after administration of any study treatment or if they started prior to study drug administration but worsened after dosing, given that worsening started within the treatment period.

Only TEAEs shall be summarized in the clinical study report. An overall summary with number and percentage of subjects with all different TEAE categories, like treatment-related, serious, leading to withdrawal, and fatal will be provided. Incidence and severity of TEAEs will be summarized within System Organ Class (SOC), and within Preferred Term (PT).

TEAEs will be summarized by relationship per SOC and PT. Relationships will be categorized into related (includes “Related”, “Possibly Related” and “Probably Related”) and unrelated (includes “Not Related” and “Unlikely Related”).

TEAEs will also be summarized by maximal severity per SOC and PT. To count the number of subjects with any TEAEs, if a subject has multiple TEAEs coded to the same PT within the same SOC, the subject will be counted once under the maximal severity.

All AEs will be listed by subject. Serious AEs (SAEs), TEAEs, and AEs leading to withdrawal will be flagged accordingly.

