### 9.1.1. Time Period and Frequency for Collecting AE and SAE Information

All AEs and SAEs will be collected from the signing of the ICF until the follow-up visit at the time points specified in the SoA ([Section 2](#)).

Medical occurrences that begin before the start of study treatment but after obtaining informed consent will be recorded on the Medical History/Current Medical Conditions section of the case report form (CRF) not the AE section.

All SAEs will be recorded and reported to the sponsor or designee within 24 hours, as indicated in [Appendix 4](#). The Investigator will submit any updated SAE data to the sponsor within 24 hours of it being available.

Investigators are not obligated to actively seek AE or SAE in former study participants. However, if the Investigator learns of any SAE, including a death, at any time after a participant has been discharged from the study, and he/she considers the event to be reasonably related to the study treatment or study participation, the Investigator must promptly notify the sponsor.

The method of recording, evaluating, and assessing causality of AE and SAE and the procedures for completing and transmitting SAE reports are provided in Appendix 4.

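### SAP 9.1 limits treatment-emergent worsening to an undefined treatment period, a limit absent from Protocol 10.3.1, so some Part B follow-up worsening can miss the TEAE tables

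*SAP*

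**What the plan says.** **TEAE definition, protocol.** Section 10.3.1 defines TEAEs as "events that started after exposure to study drug or worsened in severity after dosing". It sets no end date for either branch.

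**TEAE definition, SAP.** Section 9.1 has two branches. Events are TEAEs "if they occurred after administration of any study treatment", with no end date. Events with an earlier start are TEAEs "if they started prior to study drug administration but worsened after dosing, given that worsening started within the treatment period". SAP 6.1 (Key Definitions) does not say when the treatment period ends.

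**Which rule governs.** SAP Section 2 gives its own methods precedence over those in the protocol.

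**What is reported.** SAP 9.1 states: "Only TEAEs shall be summarized in the clinical study report". The same section puts every AE, treatment-emergent or not, in the subject listings.

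**Where pre-dose events are recorded.** Protocol 9.1.1 says "All AEs and SAEs will be collected from the signing of the ICF until the follow-up visit", yet occurrences between consent and first dose "will be recorded on the Medical History/Current Medical Conditions section of the case report form (CRF) not the AE section". SAP 9.1 says "Adverse events shall be recorded starting at signing of ICF", although the sentence before it starts AE surveillance on Day 1. Protocol Appendix 4 treats worsening of an existing condition as an AE in its own right.

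**The concern.** The two documents draw the boundary of the TEAE set differently, and the narrower one governs. The SAP's two branches are also unequal. In Cohort 1, a headache that begins on Day 9 is a TEAE. A headache recorded as an AE before dosing that first becomes more severe on Day 9 is not, if the treatment period ends before follow-up. The SAP gives no reason for treating them differently. The restriction also sits oddly with SAP 6.5, which generally resolves unclear AE start dates in favour of treatment emergence.

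The nature and severity of AEs, and the number of subjects with them, are primary endpoints in both parts. A rule that leaves out some post-dose worsening affects those tables directly.

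**Working it through.** The plan states no figure here to reproduce. The check sets the definitions side by side and measures the window they leave open.

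**Step 1. Does the treatment period include follow-up?** The Part B schedules head Treatment Period and Follow-up as separate blocks. SAP 9.1 also runs surveillance from Day 1 of the treatment period to the end of follow-up, naming the two separately. The natural reading is that follow-up lies outside, but no definition settles it.

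**Step 2. Length of the Part B window.** Nominal days come from Protocol 5.1 and the schedules. Window = follow-up visit day − last dosing day; the alternative uses the check-out day.

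| Cohort | Last dose | Check-out | Follow-up visit | After last dose | Share of Day 1 to visit | After check-out |
|---|---|---|---|---|---|---|
| 1 | Day 8 | Day 8 | Day 15 | 15 − 8 = 7 | 7/15 = 47% | 15 − 8 = 7 |
| 2 | Day 9 | Day 10 | Day 16 | 16 − 9 = 7 | 7/16 = 44% | 16 − 10 = 6 |
| 3 | Day 7 | Day 8 | Day 14 | 14 − 7 = 7 | 7/14 = 50% | 14 − 8 = 6 |
| 4 | Day 7 | Day 8 | Day 14 | 14 − 7 = 7 | 7/14 = 50% | 14 − 8 = 6 |

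Part A has no such window. Its end-of-study visit is scheduled 73 − 55 = 18 hours after Dose 9, with 3 to 72 hours allowed.

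**Step 3. Which events are affected?** Each possible course and way of recording it is put through both definitions, taking follow-up as outside the treatment period.

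| Event and how it is recorded | Protocol 10.3.1 | SAP 9.1 |
|---|---|---|
| New onset in follow-up | TEAE | TEAE (first branch) |
| Pre-dose AE record, worsens during treatment | TEAE | TEAE (second branch) |
| Pre-dose AE record keeping its original onset date, first worsens in follow-up | TEAE | Not a TEAE; listed only |
| Pre-dose condition in medical history, worsening entered as a new AE | TEAE | TEAE (first branch) |
| Pre-dose condition in medical history, worsening not entered | No AE record to classify | No AE record to classify |

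Only the third row separates the documents. It arises if pre-dose events are held as AE records, as the SAP's recording from consent implies. The fourth row arises if the protocol's medical-history rule is followed and the worsening is then entered. Neither document says whether worsening opens a new record, so the same clinical course can be counted or not according to how it is entered.

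**Step 4. Direction and size.** Every SAP TEAE is also a protocol TEAE, and the reverse fails only in the third row. The restriction can therefore remove events but never add them. With 12 subjects in a cohort, each subject lost from a row changes it by 1/12 = 8.3 percentage points, unless the subject has another TEAE counted in that row.

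**The case against.** The strongest reply is that the protocol's own filing rule largely prevents the loss. If pre-dose occurrences go to medical history and a later worsening is entered as a new AE, its onset is after dosing and the first branch counts it. This stands, and it limits the point to events kept under their original onset date. It does not remove the point, because the SAP's second branch presupposes events recorded before dosing and the documents do not say how worsening is to be entered.

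A reader might infer that all worsening in follow-up disappears from every AE table, or from the safety reporting as a whole. The documents do not support that. The loss depends on how the event is recorded. An excluded AE is still listed by subject, with seriousness and withdrawal flagged. Laboratory, vital-sign and ECG results are also summarised by visit with change from baseline, so objective changes present at the follow-up visit would still show there.

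Two further inferences are tempting. One is that the omitted window matters because partner drug is still present. In Cohorts 3 and 4 the day after the last dose is Day 8, which the schedules may place inside the treatment period, and the documents give no half-life for aspirin or clopidogrel. The other is that medical-history entries would lack a baseline grade. The documents do not describe the fields on that page. Neither argument is relied on here.

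Finally, few events will be affected in healthy volunteers. That is accepted, and it bears on priority rather than on whether the definitions agree.

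**Conclusion.** The inconsistency is real and narrow. SAP 9.1 restricts treatment-emergent worsening to a period it does not define, Protocol 10.3.1 has no such restriction, and the SAP governs. In Part B, a pre-dose event kept as an AE record with its original onset date and first worsening in the 7 days after the last dosing day (6 to 7 from check-out) would be missing from the TEAE summary tables and present only in the listings.

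This rests on two assumptions: that follow-up lies outside the treatment period, as the schedule headings suggest, and that such events are held as AE records from consent. If worsening is always entered as a new AE, nothing is lost. The expected number of affected events is small and cannot be calculated from the documents. Any error lowers the counts for a primary safety endpoint. The text should be aligned before database lock.

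**What to change.** 1. **SAP 9.1:** delete the treatment-period condition that closes the second branch of the TEAE definition, or extend it through the follow-up or end-of-study visit. Either change brings it into line with Protocol 10.3.1.
2. **Recording rule:** state that worsening of a pre-dose condition after dosing is entered as a new AE dated at the worsening, so that classification does not depend on data-entry habit.
3. **Protocol 9.1.1 and SAP 9.1:** reconcile the medical-history filing rule with recording of AEs from consent.

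The first change should not be left out. Moving pre-dose events to the AE page while keeping the condition would bring more events under the restricted branch.

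The cost is one SAP clause, one added sentence on recording, and one clarified protocol sentence. No assessment, visit or sample is added.
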